505 For each included patient, the A2ALL study coordinator will be asked to provide the
506 data, based on chart review, for a selected subset of SRTR data items. The coordinator
507 will be asked NOT to refer to copies of SRTR forms, but to provide the data based on
508 chart review (or personal knowledge) alone. These data will be entered in a web-based
509 data entry module. The module will have access to the original SRTR data, and will
510 check the new data against the original SRTR data and provide immediate feedback if a
511 discrepancy is found. The data coordinator will then resolve the difference, and either
512 confirm the new value or enter a corrected value. The original SRTR record, as well as
513 the final online entry, will be recorded in a special validation database.

514
515 The current SRTR data may be incomplete, and we have documented serious omissions
516 in the reporting of HCC data. However, because the SRTR data were submitted closer to
517 the time of listing and transplant, they may benefit from information available at those
518 times that was not documented in the patient charts. Thus, if a discrepancy is found
519 between the old SRTR data and the newly entered data, the coordinator will be given the
520 opportunity to decide which is correct.

521
522 Potential for bias may arise if the A2ALL coordinator is the same person who enters the
523 SRTR/OPTN data, or is a co-worker of that person. In that case, the A2ALL coordinator
524 may be more likely to simply validate the SRTR data, rather than checking to make sure
525 it is correct. We will attempt to minimize this bias by addressing the problem in the
526 coordinator training session. Coordinators will be instructed in the importance of
527 obtaining the data from chart review.

528 **4.5.2. Participant Selection**

529 All patients waitlisted for liver transplantation and considered for living donor
530 transplantation between 1/1/1998 and 2/28/2003 at any of the nine A2ALL centers. If
531 supplemental cadaveric transplant cases are used for any other specific aims, their data
532 may also be included in the validation study.

533 **4.5.3. Data Elements**

534 Validation of SRTR data elements will incorporate information from patients included in
535 all of the above studies.

536 **4.5.4. Sample Size and Power Calculations**

537 For an estimated proportion correct near 0.95 (95% correct), sample size of 300 will yield

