538 a 95% confidence interval (CI) for the true proportion will have a CI width of
539 approximately +/- 0.025. For estimated proportions near 0.50 (50% correct), a 95% CI
540 for the true proportion will have CI width of approximately +/- 0.057.

541 **4.5.5. Statistical Analysis**

542 The purpose of the data analysis is to document the correctness of the SRTR database.
543 For each data element we will calculate: (1) the percent missing in the original SRTR
544 data that were completed in the new data, (2) the percent of values that were not missing
545 in the original data but were changed (corrected) in the new data, and (3) the percent of
546 values that were correct in the original data. These percents should total 100%, unless an
547 original SRTR data value was deemed to be incorrect and replaced with a missing value.
548

549 An additional analysis will investigate whether data quality changed after introduction of
550 the electronic OPTN data submission system (UNet).
551

552 This validation study will tell us which of the SRTR data elements are reliable, and which
553 are not. For each data element, we will assume that the A2ALL centers are
554 representative of the other SRTR centers. Any data elements shown to be less than 95%
555 correct in the A2ALL centers should be analyzed with caution in the full SRTR database.
556

557 We will also investigate center variability, to determine if error rates are center-specific
558 or if they are similar across centers. This information will allow us to confidently use the
559 full SRTR database for selected retrospective analyses.

560 **4.6. Retrospective Post-surgical Complications Study**

561 **4.6.1. Study Methods**

562 The major objective of this portion of the study is to define the incidence of donor
563 morbidity in right lobe living donors in a retrospective cohort of patients and to compare
564 recipient morbidity after LDLT or cadaveric transplant.
565

566 The charts of all right lobe donors will be retrospectively reviewed using a defined
567 worksheet. The records of all patients who underwent a general anesthetic with the intent
568 to proceed with living donation will be included. This will allow us to capture patients
569 whose donation was aborted for various reasons. The hospital records, as well as any
570 outpatient ambulatory medical records, will be included in the review. Visits to outside

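### The SRTR validation does not plan to store the chart entry made before feedback, so any drift toward SRTR cannot be measured, and its 100% rule fails for values missing in both sources

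*Protocol*

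**What the plan says.** Protocol 4.5.1 sets up a blinded first reading: the coordinator "will be asked NOT to refer to copies of SRTR forms, but to provide the data based on" chart review or personal knowledge. The entry module holds the SRTR data and will "check the new data against the original SRTR data and provide immediate feedback if a" mismatch appears. The same coordinator then settles the difference, either standing by the entry or correcting it. Two things are listed for storage: the original SRTR record, and then "the final online entry, will be recorded in a special validation database".

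The stated reason for letting the coordinator decide is that SRTR data were submitted nearer the events and may reflect information the chart lacks. The section recognises a bias toward endorsing SRTR, but only where the coordinator, or a co-worker, also enters the SRTR/OPTN data. The remedy is training.

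Protocol 4.5.5 defines three percentages per data element: missing in SRTR and then filled in; present in SRTR but changed; and "values that were correct in the original data. These percents should total 100%, unless an" SRTR value is judged wrong and set to missing. It then treats the A2ALL centers as "representative of the other SRTR centers. Any data elements shown to be less than 95" percent correct are to be analyzed with caution in the full SRTR database. The primary aim (3.5.1) covers completeness as well as correctness. A secondary aim (3.5.2) is to decide which elements the prospective study can rely on.

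**The concern.** There are two separate defects.

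**The reading before feedback.** The first entry is the only one made without sight of the SRTR value, and it is not among the items to be stored for validation. Feedback is one-sided. Entries that disagree are reopened; entries that agree are left alone, even if both sources are wrong. A reopened entry that is changed to the SRTR value then counts as an SRTR value that was correct. The stored pair cannot show whether agreement was there from the start or came after the prompt. If the first entry is not saved, no later analysis can recover it, and nobody can check whether the training worked.

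**The 100% rule.** A value absent from both SRTR and the chart was not filled in, not changed and not correct. It fits none of the three categories and is not the listed exception. The protocol makes the case foreseeable: 4.5.1 reports serious gaps in SRTR reporting of HCC, and 4.2.3 warns that chart information may be missing.

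At stake are the 95% threshold, the choice of elements for the prospective study, and the completeness half of the primary aim.

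**Working it through.** **1. The plan's own figures.** Section 4.5.4 begins: "For an estimated proportion correct near 0.95 (95% correct), sample size of 300 will yield" a 95% interval of about ±0.025, and about ±0.057 at 0.50. The half-width is 1.96 × √(p(1−p)/300).

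- p = 0.95: 0.0247
- p = 0.50: 0.0566

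Both reproduce. They describe sampling error only.

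**2. Effect of feedback.** The documents give no accuracy, chart-error or reversion rates, so all inputs here are assumed. Let A be true SRTR accuracy, e the chart-abstraction error rate (independent of SRTR error, and never producing the same wrong value), r_W the share of discrepancies reverted to SRTR when SRTR is wrong, and r_R the share reverted when SRTR is right.

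- Agreement before feedback = A(1−e)
- Agreement after feedback = A(1−e) + A·e·r_R + (1−A)·r_W

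The added terms cannot be negative. A flagged entry changed to some third value, or to missing, still disagrees. So agreement after feedback is at or above agreement before it.

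With A = 0.93:

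| e | r_R | r_W | Before feedback | After feedback | After minus true 93% (points) |
|---|---|---|---|---|---|
| 0 | – | 0.3 | 93.0% | 95.1% | +2.1 |
| 0 | – | 0.5 | 93.0% | 96.5% | +3.5 |
| 0.05 | 1 | 0 | 88.4% | 93.0% | 0.0 |
| 0.05 | 0.3 | 0.3 | 88.4% | 91.8% | −1.2 |
| 0.05 | 0.5 | 0.5 | 88.4% | 94.2% | +1.2 |
| 0.05 | 1 | 0.3 | 88.4% | 95.1% | +2.1 |

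Example, first row: 0.93 + 0.07 × 0.3 = 0.951. Example, fourth row: 0.8835 + 0.1165 × 0.3 = 0.918. When all discrepancies are reverted at one common rate and e = 0.05, the bias turns positive above (0.93 − 0.8835)/0.1165 ≈ 40%.

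The positive shifts of 2.1 to 3.5 points are about as large as the 2.5-point half-width in step 1, and a larger sample does not reduce them.

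**3. Values missing in both sources.** Let m be the share missing in both. Assume 3% filled in from the chart, 4% changed, and none replaced by missing. Correct records are then 1 − m − 0.03 − 0.04 of the total.

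| m | Three categories sum to | Correct / all records | Correct / three categories | Correct if m counted as correct | Originally complete / all | Originally complete / three categories |
|---|---|---|---|---|---|---|
| 2% | 98% | 91% | 92.9% | 93% | 95% | 96.9% |
| 5% | 95% | 88% | 92.6% | 93% | 92% | 96.8% |
| 10% | 90% | 83% | 92.2% | 93% | 87% | 96.7% |
| 20% | 80% | 73% | 91.3% | 93% | 77% | 96.3% |

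Counting m as correct would put completeness at 100% − 3% = 97% in every row. A further possible denominator is records with a non-missing SRTR value: at m = 10% this gives 0.83/0.87 = 95.4% correct. One set of data can therefore read as 83%, 92%, 93% or 95% correct, depending on an unstated denominator.

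**The case against.** The strongest objection is to the tempting conclusion that SRTR accuracy *will* be overstated. That conclusion treats the chart abstraction as error-free. The protocol gives grounds to think otherwise, and letting the coordinator settle differences is its reasoned answer. With 5% chart error and 30% of discrepancies reverted, the result understates true accuracy (91.8% against 93%). With perfect adjudication there is no bias. This objection stands.

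It also defeats a natural remedy, making the blinded entry the main result. That entry measures chart–SRTR agreement and charges every abstraction slip to SRTR: 88.4% against a true 93% on the same inputs, further off than any adjudicated result in the table.

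Three other inferences are not supported:

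- A reader might infer that the first entry is destroyed. The protocol says only what enters the validation database. Section 7.4 describes a log of all database modifications, which may hold it. But that log is described for access monitoring and audit, is not named as an analysis source, and may not capture an entry changed before it is saved.
- A reader might infer that the plan admits a general tendency to endorse SRTR. The admission is limited to the same-person or co-worker case.
- A reader might infer that the 95% figure is a pass mark. It triggers caution in the full SRTR database, and the aim on prospective use states no threshold.

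Finally, denominators and table rows are often left to an SAP, and with all records as the denominator nothing is inflated; the sum simply falls short of 100%. That is fair as far as it goes. But this protocol itself fixes what is stored and states a total that is wrong.

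**Conclusion.** The point holds in a limited form. The stored validation data cannot show how far agreement moved after coordinators saw the discrepancy, so percent correct may be overstated by an unmeasurable amount. Neither direction nor size can be settled from the documents. For a true 93%, the assumed scenarios run from 1.2 points too low to 3.5 points too high, enough to fall either side of 95%.

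The 100% statement is wrong as written whenever any value is missing in both sources. Inflation follows only if such values are dropped or counted as correct. In that case, at an assumed 10% missing in both, completeness goes from 87% to about 97%, and percent correct from 83% of all records to 92–93%.

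This concerns a descriptive sub-study and does not touch the survival objective. It should be corrected before data entry, because an entry that was never saved cannot be analyzed later.

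**What to change.** 1. In 4.5.1, add the first chart-based entry, made before any feedback, as a third value in the validation database.
2. Keep the adjudicated value as the correctness result. Beside it, report agreement before and after feedback and the share of discrepancies reverted to the SRTR value, as a sensitivity check for elements near 95%.
3. In 4.5.5, add categories for missing in both sources and for SRTR values replaced by missing, so that the categories do total 100%.
4. State the denominators: completeness over all records, correctness over records with a non-missing original SRTR value.

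The cost is one stored field and a slightly longer table. Some elements may look less reliable than under the current plan.

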215 either respect. Sample records will be examined for completeness and ease of obtaining
216 information on all data elements before formal data collection begins.

217

218 a. At listing

219 Date of listing

220 DOB, sex, ethnicity (PHS categories)

221 Reasons for transplantation (list primary and secondary diseases)

222 MELD/UNOS status/CTP score at time of listing

223

224 b. Potential Donor

225 Date of each donor evaluation

226 Information on potential donor. Data collection on donors will largely be limited to
227 clinically significant pre- and post-donation events and a small amount of operative
228 information.

229 Donor outcome information

230 Reasons for not donating for those who do not donate

- 231 - Medical or psychological for donor
 - 232 o Medical condition (liver related vs. co-morbid medical conditions)
 - 233 o Anatomical
 - 234 o Size
 - 235 o Blood type
 - 236 o Psychological
- 237 - Donor declines/changes mind
- 238 - Recipient became too sick (or too well)
- 239 - Recipient received cadaveric transplant
- 240 - Other

241 Date of decision not to donate

- 242
243 c. Pre-transplant
244 Complications (treated ascites, treated SBP, variceal bleed, other GI bleeds requiring
245 transfusion, hepatorenal, hepatopulmonary, treated encephalopathy, TIPS,
246 portopulmonary hypertension, bony fracture [yes or no for each])
247 SBP Prophylaxis (yes/no)
248 Antiviral therapy (specific to HBV and HCV)
249 Changes in MELD, CTP, OPTN/UNOS status
250 Hospitalization admission and discharge date
251 Days in ICU
252 Death
253 Dates for each of these
254
255 d. Transplantation and beyond
256 Date of transplant
257 Selected intra-operative data
258 Hospitalization dates
259 Days in ICU
260 Retransplantation
261 Baseline immunosuppression regimen (tacrolimus, cyclosporine, or non-calcineurin
262 antagonist based); antibody induction (yes/no)
263 Treated rejection episodes within one year of transplant:
264 1. Date of rejection (treated rejection episodes separated by less than 22 days will be
265 considered the same event for analysis purposes).
266 2. Liver biopsy (when performed): Acute rejection severity as recorded in the
267 original pathology reading (mild, moderate, severe or undetermined)
268 3. Immunosuppression at transplant and at the initiation of anti-rejection therapy
269 4. Drugs used to treat rejection

270 **4.2.4. Sample Size and Power Calculations**

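### The SRTR validation judges each element by percent correct alone, so for any numeric or date element it ignores how large the errors are

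*Protocol*

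**What the plan says.** Protocol 4.5.5 prescribes the same tally for every element: "For each data element we will calculate: (1) the percent missing in the original SRTR" data and later filled in; the percent present "in the original data but were changed (corrected) in the new data, and (3) the percent of" values found to be right. The classes are meant to be exhaustive: "values that were correct in the original data. These percents should total 100%, unless an" incorrect original is replaced by a missing value. The section then says the study will show which elements are reliable and which are not. Elements under 95% "correct in the A2ALL centers should be analyzed with caution in the full SRTR database".

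The tally is produced as described in 4.5.1. The coordinator enters data from the chart, and the entry module will "check the new data against the original SRTR data and provide immediate feedback if a" mismatch appears. The coordinator then has the "opportunity to decide which is correct". The original SRTR record and the final entry are both stored.

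4.5.5 plans two further analyses, one of data quality before and after UNet and one of error rates between centers. Neither is said to use error size. The validated items are called a selected subset and are not listed. The study's own data elements in 4.2.3 include the date of listing and "MELD/UNOS status/CTP score at time of listing".

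**The concern.** For a categorical item, right or wrong is the natural measure. For a score or a date, usefulness depends on how far off the wrong values are as well as how many there are. A listing date one day out and one a year out each add one to the changed class, and the 95% mark cannot tell them apart.

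The validation is meant to support real uses. Aim 3.5.2 asks which OPTN elements can be relied on in the prospective study, and 4.5.5 expects to use the full SRTR database with confidence for selected analyses. Elsewhere the protocol adjusts for MELD (4.1, 4.6.2) and selects supplemental controls from SRTR, matched on transplant date within six months (4.6.2). A one-day date error would almost never disturb that match; a one-year error would. A reliability call that can rank elements in the opposite order to their actual error is a weak basis for these uses.

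**Working it through.** **1. The plan's own figures.** 4.5.4 gives 95% CI half-widths for n = 300. From 1.96 × √(p(1−p)/n):
- p = 0.95: 1.96 × √(0.95 × 0.05/300) = 0.0247 (stated 0.025).
- p = 0.50: 1.96 × √(0.25/300) = 0.0566 (stated 0.057).

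Both reproduce. The precision is not in question; the issue is what is being estimated.

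**2. Two date elements, n = 300 (assumed error patterns).** With k wrong values, each off by e days: percent correct = 1 − k/n; mean absolute error = k·e/n; RMS error = e·√(k/n).

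| Element | k | e (days) | Percent correct | 95% mark | Mean absolute error (days) | RMS error (days) |
|---|---|---|---|---|---|---|
| A | 24 | 1 | 92% | flagged | 24 × 1/300 = 0.08 | √0.08 = 0.28 |
| B | 12 | 365 | 96% | passes | 12 × 365/300 = 14.6 | 365 × √0.04 = 73 |

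**3. A MELD-like score (assumed distribution).** Take whole-number scores, normal with mean 15 and SD 6, kept within 6 to 40. Simulating 2,000,000 values gives, after truncation, mean 15.73, SD 5.35 and variance 28.63. The slope factor is cov(recorded, true)/var(recorded), the fraction of a regression slope that survives when the recorded value is used.

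- *10% off by one point, either direction.* RMS = √0.10 = 0.32. Slope factor = 28.63/(28.63 + 0.10) = 0.997. Percent correct 90%: flagged.
- *4% hold another patient's value.* RMS = √(0.04 × 2 × 28.63) = 1.5. The variance is unchanged and the covariance is multiplied by 0.96, so the slope factor is 0.96. Percent correct about 96%: passes.
- *4% hold an arbitrary value, uniform on 6 to 40* (mean 23, variance (35² − 1)/12 = 102). Mean squared error = 0.04 × [(23 − 15.73)² + 102 + 28.63] = 0.04 × 183.5 = 7.34, so RMS = 2.7. Recorded variance = 0.96 × 28.63 + 0.04 × 102 + 0.04 × 0.96 × 7.27² = 27.48 + 4.08 + 2.03 = 33.59. Slope factor = 27.48/33.59 = 0.82. Percent correct about 96%: passes.

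The simulation agrees with these formulas. If scores outside 6 to 40 are set to the limit rather than dropped, the two gross-error patterns give RMS 1.6 and 2.8 and slope losses of 4% and 17%.

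**4. Would a tolerance alone cure it?** The percent within a tolerance can never be lower than the percent that match exactly. In the simulation, within ±1 point gives 100% for the first pattern, 96.6% for the second and 96.3% for the third. Moving the 95% mark to this percent clears the harmless element and still passes both harmful ones.

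**5. Would a size summary separate them?** Mean and SD of the difference are 0 and 0.32 for the first pattern, and 0 and 1.5 for the second. For the third the mean is 0.04 × 7.27 = 0.29 and the SD is √(7.34 − 0.29²) = 2.7. These put the three patterns in the right order.

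**The case against.** The tally fits the stated purpose of documenting correctness, and its missing class directly measures the one SRTR fault that the protocol names, omitted HCC data. Size-of-error summaries are often left to an analysis plan or manual, and both values are stored, so they could be produced without amending anything. This stands in part. Nothing in 4.5.5 is miscalculated or contradictory. But the section does more than leave detail open: it fixes an exhaustive classification and a cut-off and draws a reliability conclusion from them.

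Coordinator judgment might also be thought to absorb trivial differences. A mismatch does count as changed only if the coordinator keeps a value other than the SRTR one. However, the question put is which value is right, not whether the difference matters. Any informal tolerance would vary between coordinators and could show up as center variability.

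Several stronger readings are tempting, and the protocol does not support them:
- *That values are scored only as right or wrong.* There is a third class for missing-then-completed values.
- *That sound elements would be discarded, or that 95% decides what enters the prospective study.* The mark calls only for caution in the full SRTR database. The protocol does not tie it to the choice of prospective elements, and it does not say that elements above the mark escape further scrutiny.
- *That MELD, CTP and the listing date are definitely validated.* The subset is not listed, and these items come from the mortality study's data list.
- *That a slope loss of 17% or 18% is to be expected.* That is the more extreme of two assumed gross-error patterns; the other gives 4%. No figure in the protocol supports either.

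**Conclusion.** The point holds as a minor improvement. For any numeric or date element in the validated subset, the rule in 4.5.5 can flag an element with negligible error and pass one with substantial error. In the illustration, 90% correct goes with an RMS error of 0.3 and under 1% slope loss, while about 96% correct goes with an RMS error of about 1.5 to 2.7 and a slope loss of about 4% to 18%.

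The possibility of reversal follows from the rule itself. Its size rests on assumed score distributions and error patterns, and its relevance rests on the inference that scores or dates are among the validated items. Percent correct remains suitable for categorical elements.

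**What to change.** In 4.5.5:

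1. Keep the three-class tally and the exact percent correct for all elements.
2. For numeric and date elements, add the mean and SD of the difference (original SRTR value minus the final chart-based entry) and the percent of values beyond a gross-error limit fixed in advance for each element.
3. Call such an element reliable only if it meets the 95% mark and its size-of-error summary is also acceptable. Where percent correct falls below 95%, state whether the differences lie within a tolerance fixed in advance.
4. Do not replace the 95% mark with the within-tolerance percent alone, since that can only make the rule more lenient.

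It would also help to list the validated items by type, so that it is clear where the addition applies.

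The cost is a short table of tolerances and gross-error limits, agreed before the data are examined, and a few extra summary columns. No new data are needed, because the validation database already holds both values.

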110 To ascertain which data elements collected via the OPTN data collection process can be
111 reliably employed for use in the prospective A2ALL Cohort Study.

112
113 To provide feedback to the SRTR and OPTN on the accuracy and completeness of
114 selected data elements.

115 **3.6. Retrospective Post-surgical Complications Study**

116 **3.6.1. Primary Aim**

117 To determine the rate of the major donor post-operative complications associated with
118 planned right lobe liver donation

119

120 To compare the major recipient post-operative complications after LDLT versus
121 cadaveric transplant.

122 **3.7. Retrospective Resource Utilization Study**

123 **3.7.1. Primary Aim**

124 To compare the resource utilization for patients who proceed to LDLT versus those for
125 whom living donation does not occur and thus proceed toward cadaveric transplant.

126 **4. Investigational Plan**

127 **4.1. Overall Study Design**

128 Most of the specific aims require LDLT recipients and control patients who did not
129 undergo LDLT. However, the identification of these controls and study start time (time
130 0) for following LDLT patients and controls will differ for the various objectives. All, or
131 nearly all, of the LDLT recipients will be included in all analyses, which will simplify
132 chart review. Many of the control patients will also be included in several analyses.
133 LDLT donors will be evaluated for surgical complications.

134

135 For the primary survival and resource utilization objectives, the study entry point is at
136 initial evaluation of a potential living donor that includes history and physical
137 examination at the transplant center. The overall design of the retrospective cohort study
138 is predicated on this definition as the starting point for inclusion in the cohort. In the
139 primary analysis (see below), the mortality of LDLT patients will be compared to
140 mortality of patients who have not yet had LDLT, regardless of subsequent events
141 (cadaveric transplant, death, or removal from waitlist for any other reason). This cohort
142 will include all those evaluated for LDLT transplants from 1/1/98 until 2/28/03. Among
143 the 9 transplant centers in the A2ALL project, approximately 40% of individuals who had
144 a potential living donor identified went on to undergo LDLT, leaving 60% as controls
145 (see Feasibility Study report [Appendix A]). Based on this report, we estimate that

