469 cadaveric transplant recipients, no supplemental contemporaneous cadaveric controls will
470 be used.

471 **4.4.3. Data Elements**

472 Maximum size and number by radiology pre-transplant and at transplant (explant)
473 Whether Milan criteria were met
474 Whether HCC was an incidental finding.
475 Date of diagnosis of disease recurrence post-transplant.
476 Number and type of HCC ablation procedures.

477 **4.4.4. Sample Size and Power Calculations**

478 We anticipate approximately 75 hepatocellular carcinomas among the ~ 300 LDLT cases,
479 and approximately 125 among the ~ 500 non-LDLT cases who were also evaluated for
480 LDLT. With 75 LDLT cases and 125 non-LDLT cases, we will have 90% power to
481 detect a difference in recurrence (or presence) of HCC of 10% versus 30%. Since
482 reduction of HCC in the non-LDLT group will be due to subsequent cadaveric
483 transplantation, this statistical test will compare the strategy of LDLT versus waiting for a
484 cadaveric transplant.

485 **4.4.5. Statistical Analysis**

486 Initial analysis of HCC will be primarily descriptive. The characteristics of HCC patients
487 described will include TNM explant pathologic stage, use of ablation pretransplant, and
488 pre transplant ablation method (i.e. chemoembolization, RFA, etc.). The proportion
489 recurring within one year will be presented, with 95% CI. Predictors of one-year
490 recurrence will be explored using logistic regression for patients with at least one year of
491 follow-up. The difference between recurrence (or presence) proportions for LDLT versus
492 non-LDLT patients will also be estimated using a 95% confidence interval. A comparison
493 of survival between these two groups will be performed using Cox regression, adjusted
494 for various prognostic covariates. A comparison of survival between LDLT and
495 cadaveric transplant recipients will also be performed.

496 **4.5. SRTR Data Validation Study**

497 *(This section does not apply to subjects who have the first living donor evaluated after*
498 *2/28/03)*

499 **4.5.1. Study Methods**

500 We will investigate records for all patients with LDLT, and a subset of patients not
501 receiving LDLT. These patients will be selected as needed to develop comparison
502 cohorts for the other Retrospective research aims. All patients to be studied as part of
503 any Retrospective cohort will be included in this validation study.

504

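### The 95% line in the SRTR validation study is applied to overall percent correct, so for yes/no elements and diagnosis categories the share of true cases that may be missing depends on prevalence: one in five for HCC, more for rarer items

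*Protocol*

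**What the plan says.** Section 4.5.5 of the Protocol defines three percentages for each element: blank in the registry and then filled in, present but changed, and correct. They share a denominator, because the third is the percent of "values that were correct in the original data. These percents should total 100%, unless an" incorrect registry value is replaced by a blank. The section then states: "This validation study will tell us which of the SRTR data elements are reliable, and which" are not. The only number attached to that statement is the caution line: "Any data elements shown to be less than 95" percent "correct in the A2ALL centers should be analyzed with caution in the full SRTR database". The further analyses named there compare data quality before and after electronic submission and between centers. Neither splits the records by true status.

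Section 4.5.1 says which kind of error is already known: "The current SRTR data may be incomplete, and we have documented serious omissions" in HCC reporting. Section 4.4.4 gives the prevalence: "We anticipate approximately 75 hepatocellular carcinomas among the ~ 300 LDLT cases", and about 125 among some 500 non-LDLT cases. Section 3.5.2 names a use of the results, namely to learn which elements can be "reliably employed for use in the prospective A2ALL Cohort Study".

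**The concern.** In a yes/no field most patients may be true negatives, and a registry that records them correctly earns a high percent correct whatever it does with the positives. The error that Section 4.5.1 reports, omission, is the one this measure dilutes. None of the three planned percentages answers what a user of the registry needs to know: of the patients whose charts confirm the condition, what share does the registry hold?

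The same 95% is therefore a different standard for each element, and it becomes more lenient as the condition becomes rarer. An element could be read as reliable while a material share of its cases is absent. Anyone using it to find cases or to estimate frequency in the full registry would then carry that loss forward without a warning.

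**Working it through.** **Inputs**
- Caution line: 95% correct (4.5.5).
- Validation sample: n = 300 (4.5.4). The evaluated cohort is about 800 (4.1), and both sizes are used below.
- HCC prevalence: 75/300 = 25% and 125/500 = 25%, so 200/800 overall (4.4.4).
- HCV prevalence: about 1/3 (4.3.4).
- Prevalences of 10% and 5% are assumptions. The Protocol gives none for other elements.

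**The plan's own figures.** The half-width is 1.96 × √(p(1 − p)/300). At p = 0.95 it is 0.0247 (stated 0.025) and at p = 0.50 it is 0.0566 (stated 0.057). Both reproduce.

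**Overall percent correct for a yes/no element**

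correct = 1 − prevalence × (1 − sensitivity) − (1 − prevalence) × (1 − specificity)

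With omissions only (specificity = 1) this becomes 1 − prevalence × share missed. Setting it to 0.95 gives the largest tolerated share missed: min(1, 0.05/prevalence).

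| Prevalence | Source | Tolerated share missed |
|---|---|---|
| 1/3 (HCV) | 4.3.4 | 0.05/0.333 = 15% |
| 25% (HCC) | 4.4.4 | 0.05/0.25 = 20% |
| 10% | assumed | 0.05/0.10 = 50% |
| 5% or less | assumed | 100% |

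In counts for HCC, 5% of 300 is 15 errors among 75 cases, and 5% of 800 is 40 errors among 200 cases. Both are 20%.

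**Chance that an element is not flagged.** This is the probability that the observed percent correct is at least 95%, from a binomial with success probability 1 − prevalence × share missed.

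| Prevalence, share missed | True percent correct | n = 300 | n = 800 |
|---|---|---|---|
| 25%, 15% | 96.25% | 0.90 | 0.97 |
| 25%, 18% | 95.5% | 0.72 | 0.78 |
| 25%, 20% | 95.0% | 0.57 | 0.54 |
| 25%, 25% | 93.75% | 0.22 | 0.08 |
| 25%, 30% | 92.5% | 0.06 | 0.003 |
| 10% (assumed), 40% | 96.0% | 0.85 | 0.93 |
| 5% (assumed), 80% | 96.0% | 0.85 | 0.93 |

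**If "Any data elements shown to be less than 95" percent requires the upper 95% confidence limit to lie below 0.95**, more errors go unflagged. At n = 300, 23 errors (exact limit) or 24 (Wald limit) escape, which is 31% or 32% of 75 HCC cases. At n = 800, 52 or 53 errors escape, which is 26% or 26.5% of 200.

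**Precision of sensitivity**, by 1.96 × √(s(1 − s)/positives):
- 75 positives: ±0.049 at s = 0.95 and ±0.091 at s = 0.80.
- 200 positives: ±0.030 at s = 0.95 and ±0.055 at s = 0.80.

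**The case against.** - **HCC is not a rare item.** This stands. At 25% prevalence the line catches serious under-recording: with 30% of cases missing, HCC escapes the flag with probability 0.06 at n = 300 and 0.003 at n = 800. A reader might infer that the rule would pass HCC however badly it is recorded. The plan's figures do not support that.
- **The line is a one-directional caution.** This also stands. Section 4.5.5 excludes nothing and does not say that 95% or more certifies an element. A reader might infer that the line decides which elements enter the prospective cohort, but Section 3.5.2 does not tie selection to it. The remark about using the full registry with confidence follows the sentence on center variability, not the 95% line. What remains is that the section promises to separate reliable from unreliable elements and gives no other number for doing so.
- **Blank fields already count against an element.** True: they appear as the first percentage and reduce percent correct. They draw on the same 5% allowance as false negative entries, so the ceiling on missed cases is unchanged.
- **The uses within this study are guarded.** Largely true. Section 4.3.1 allows HCV patients to be identified at the facility if the registry is incomplete, and Section 4.3.3 requires a positive HCV RNA report. Section 4.4.2 uses no supplemental cadaveric controls for HCC. The exposure is mainly in later use of the registry.
- **The largest losses rest on assumed prevalences.** They do. The validated items are an unlisted subset, so nothing shows that a 5% or 10% item is among them.
- **Sensitivity is detail for an analysis plan.** This does not stand. The Protocol itself fixes the statistic, the line and the inference.
- **A hard 95% cut on sensitivity would be noisy.** This stands and shapes the fix. With 15 positives, one omission gives 14/15 = 93.3%, so an element with true sensitivity of 97% would be flagged with probability 1 − 0.97^15 = 0.37.

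**Conclusion.** The concern holds in a limited form. Overall percent correct against 95% is the only criterion in Section 4.5.5, and for yes/no elements and diagnosis categories it does not bound the share of true cases missing from the registry. On the plan's own prevalences, up to 20% of HCC cases or 15% of HCV cases can be absent at 95% correct. On assumed prevalences the figure is half at 10% and all at 5% or less.

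These are worst cases: they assume omissions only, and any false positive or other error uses part of the same 5%. If a flag needs the upper confidence limit below 95%, the HCC figure rises to about 26–32%. The conclusion is that a moderate loss of HCC cases, and possibly a large loss for rarer items, can go unflagged. The change is worth making but does not affect the study's design.

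**What to change.** In Section 4.5.5, for yes/no elements and individual diagnosis categories:

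- Report sensitivity (the share of chart-confirmed positives that the original SRTR data recorded) and positive predictive value (the share of SRTR positives that the chart confirms). Take the final resolved value as reference and give each an exact 95% confidence interval.
- Do not call such an element reliable on overall percent correct alone. Base the caution on these two measures read with their intervals.
- Report elements with few positives as imprecise, instead of applying a hard 95% cut to the point estimate.

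Overall percent correct can stay for dates, continuous values and common multi-category fields.

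In Section 4.5.4, state that precision for these measures depends on the number of positives, not on 300: for HCC at 95% sensitivity, about ±0.049 with 75 cases and ±0.030 with 200 (normal approximation; exact intervals will differ somewhat).

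No new data are needed, because Section 4.5.1 already stores the original record and the final entry. The cost is a few more tabulations, wider intervals and more elements flagged.
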